B.7. Direct-acting antiviral HCV agents and resistance. Emergence of antiviral resistant variants during PI-based therapy has been observed during all trials, and is associated with both virological failure and relapse.¹¹⁵ In clinical trials, resistance-associated mutations were seen in 62% of patients who failed to achieve SVR. However, only 5% of patients in telaprevir trials had baseline HCV substitutions/variants, and these were not associated with SVR.¹¹⁵ Treatment-emergent substitutions have been demonstrated to reduce the anti- HCV activity of NS3/4A protease inhibitors.¹¹⁶⁻¹¹⁸ Additional mutations have been seen in patients treated with fixed-dose (ledipasvir and sofosbuvir). In the proposed trial, we will assess development of resistance, and determine the association between adherence level and development of resistance.

B.8. Cost of HCV treatment. A 48-week course of IFN, ribavirin, and telaprevir, including the use of growth factors (and exclusive of physician visits, laboratory tests, or care for complications) may be over \$50,000.^{119,177-179} Cost of fixed-dose (ledipasvir and sofosbuvir) may be over \$90,000. A small increment in the overall cost of treatment that appreciably increases patients' likelihood of successfully completing the regimen could substantially improve its cost-effectiveness. To assess this, we will estimate the cost of each model of on-site care (mDOT, CGT, and standard care). While intensive on-site interventions such as mDOT and CGT may require additional provider time, we expect the incremental cost of this effort will be relatively small compared to the current cost of treatment.

[figure not shown]
B.9. Theoretical frameworks for the proposed trial.

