D.9.6. Future developments in HCV treatment. Study participants will receive state-of-the-art treatment (IFN in combination with telaprevir and ribavirin). As additional regimens become available with either more convenient dosing, fewer side effects, or increased efficacy, participants in all 3 arms will receive treatment according to best available practices. On October 10, 2014, the FDA approved fixed-dose (ledipasvir and sofosbuvir). Because rates of SVR are >95% in patients initiating treatment with fixed-dose (ledipasvir and sofosbuvir), all newly enrolled subjects will initiate treatment with this regimen. It is likely that our intensive models of care will be generalizable to IFN-sparing regimens which include only oral therapies. We recognize that HCV treatment has been greatly simplified, but issues with adherence, resistance, side effects, and cost will remain.

D.10. Data sources and collection.

D.10.1. Overview. Sources of data will include: blood and urine tests, participant interviews, medical charts, staff activity and expense logs, direct observation of staff, and electronic adherence monitors (Table 3).

D.10.2. Research visits. Research visits will occur at baseline, then every 4 weeks during the first 12 weeks of treatment, then at week 24 (if necessary), a “Final Treatment Week visit” will be conducted after the last day of treatment, and then post-treatment visits after 4, 12, and 24 weeks, for a total of up to 9 research visits. Participants will receive \$25 for each visit and an additional \$20 for visits with blood draws.

Baseline visit (Table 3). At baseline we will assess: sociodemographic and HCV clinical factors, potential mediating variables based on the IMB model, potential moderators (including psychiatric status, substance use, and unstable housing), and additional psychosocial factors hypothesized to predict adherence. The baseline visit will take approximately 3 hours. Blood will be collected at the first visit and stored for possible HCV viral load and resistance testing, and for future studies.

Follow-up visits (Table 3). Follow up visits will occur at weeks 4, 8, 12, and 24 (if necessary).

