For the analysis of repeatedly measured adherence (using 6 post-baseline time points and adherence as a continuous measure), we will apply mixed effects linear model to test if the 3 groups are significantly different. This model accounts for within-subject longitudinal outcome correlation by taking the subject-level intercept as random. The model will include potential confounding variables. If the omnibus equality test is rejected, we will conduct the 2 post-hoc pairwise tests described above. Concerning potential clustering effects in the CGT arm, we used pilot data (5 groups) to examine whether clustering influenced adherence. Between cluster variation was not significant, as tested by application of a random effects repeated-measure ANOVA model. Clustering in the GCT arm will be minimal, and we will not adjust for it in statistical or power analysis.

We will also apply mixed effects logistic regression to test the significance of mDOT and CGT on repeatedly-measured undetectable HCV VL throughout the intervention period, adjusting for substance use. Changes in illicit drug use will be analyzed using urine toxicology data from each visit, counting the “person-month” as a unit of analysis, and analyzing the proportion of person-months that are positive for use of illicit drugs using a chi-square analysis.

As secondary analyses, we will examine if mDOT and CGT effects, v. TAU, will be mediated by IMB components. We will assess IMB model mediators of adherence at baseline, and during the intervention, and will analyze changes in those variables from the baseline to the intervention period. The indirect effects of IMB mediators will be tested by assessing changes in coefficients of the intervention effect (mDOT or CGT) with and without IMB component(s) in mixed effects models. Confidence intervals of the mediated effects will be calculated by bootstrapping, and mediation assumed if confidence intervals do not include zero.

D.12.3. Hypotheses for Aim 2. We hypothesize that only a minority (~20%) of IDUs will develop resistance, and that the relationship between adherence and resistance will be quadratic.

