D.12.4. Analytic plan for Aim 2. The proportion of participants (n=150) who develop resistance will be determined with 95% confidence interval (CIs) calculated using exact binomial methods. The proportion of participants with resistance will then be determined within each of 4 groups determined by quartiles of adherence measured at the final time point in the study. We will apply logistic regression models to estimate odds ratios for resistance in each quartile. To examine whether the relationship between adherence and resistance is quadratic, we will test a linearity of trends in odds ratios. If this linear trend is rejected, we will identify a quartile group that is associated with the highest odds of resistance. Potential covariates will be entered in regression models if found by univariate analysis to be associated ($p<0.2$) with resistance.

D.12.5. Hypotheses for Aim 3. We hypothesize that the total cost of delivering the CGT intervention will be lower than delivering the mDOT intervention, and that the incremental cost-effectiveness ratios for CGT v. TAU and mDOT v. TAU will each be less than \$100,000/QALY.

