Adherence. Based on our pilot data, if we conservatively assume that 80% of subjects in both mDOT and CGT arms will achieve $\geq 80\%$ adherence (v. 50% in the TAU arm), we will have $> 87\%$ power to find a statistically significant difference. With the application of mixed-effects logistic regression to the repeatedly measured binary adherence outcome, power will be greater than 87% no matter how large the within-subject outcome correlation or intraclass correlation (ICC).

In our previous DOT study, mean adherence in the mDOT group was 87% (SD=12%, n=21), and mean adherence in the TAU group was 77% (SD=20%, n=19) which translates into a standardized effect size or Cohen's $d = 0.6$. Based on this effect size, the power of the mixed effects linear model for the repeatedly measured continuous adherence outcome will be greater than 90%, even if anticipated ICC is as high as 0.5.

Treatment completion. Based on our pilot data, if we assume treatment completion rates of 85% in CGT, 60% in mDOT, and 50% in TAU, we will have $> 80\%$ power to detect this difference.

SVR. We anticipate that SVR rates in the mDOT and CGT arms will be 70%, and $\leq 40\%$ in the TAU arm.^{13,70,82} The statistical power will be $> 80\%$. These are conservative estimates of effect sizes, as actual effect sizes will likely be larger because regimens now contain telaprevir which is taken 3x daily. Effects size for fixed-dose (ledipasvir and sofosbuvir) is likely to be lower.

Resistance. We estimate that 16% of intervention arm subjects v. 30% of TAU subjects will develop resistance. We are underpowered to detect this difference, and consider this an exploratory analysis.

Effectiveness of intensive models of care. We will determine the proportion (and 95% CI) of subjects in each of the intensive intervention arms to achieve SVR, and compare to results from large registration trials.

D.14. Limitations. In addition to the considerations noted in Section D., our results may not be generalizable to HCV-infected drug users not enrolled in methadone clinics. However, we believe that the intensive models we are testing, if efficacious, can and should be adopted in diverse settings and populations.

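### Aim 2 carries two incompatible expectations for resistance events (31, or about 11–18), and the uncapped quartile-plus-screening model would be sparse at the lower one

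*Combined protocol and SAP*

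**What the plan says.** **Aim 2 model.** D.12.4 pools all participants: "The proportion of participants (n=150) who develop resistance will be determined" with an exact confidence interval. Resistance is then tabulated "within each of 4 groups determined by quartiles of adherence", and "We will apply logistic regression models to estimate odds ratios for resistance in each quartile". A test of linear trend follows; if it is rejected, the quartile with the highest odds is named. On adjustment: "Potential covariates will be entered in regression models if found by univariate analysis to be associated" with resistance, at p<0.2. There is no cap on covariates, no expected event count and no fallback for sparse data.

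**Expected resistance.** D.12.3 expects that "only a minority (~20%) of IDUs will develop resistance" and that the adherence–resistance relationship is quadratic. D.13 adds: "We estimate that 16% of intervention arm subjects v. 30% of TAU subjects will develop resistance". It calls that between-arm comparison underpowered and exploratory.

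**Regimens.** D.7 places 100 of the 150 participants on fixed-dose ledipasvir–sofosbuvir. D.9.6 states that "rates of SVR are >95% in patients initiating treatment with fixed-dose" ledipasvir–sofosbuvir. D.1.4 cites 75% SVR with the earlier regimen. B.7, discussing protease-inhibitor and telaprevir trials, reports that "resistance-associated mutations were seen in 62% of patients who failed to achieve SVR". D.13 concedes that the effect size is likely to be lower with the new regimen, but revises no rate.

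**The concern.** The resistance rates appear to predate the change of regimen. D.13 justifies its SVR assumptions by reference to telaprevir, while two thirds of the sample takes a regimen for which the document expects few failures. D.10.4 draws most resistance results from participants without SVR or with a viral load of at least 2000 IU/ml, so fewer failures should mean fewer observable resistance events.

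The model is sensitive to that number. Four quartile groups plus an open-ended screen can use up the available information quickly. With few events, a quartile may contain none, and its ordinary logistic odds ratio is then zero or infinite. Screening at p<0.2 admits about one in five irrelevant candidates, and the final tests take no account of the selection. What is at stake is the principal Aim 2 result: the shape of the adherence–resistance relationship and the quartile named as having the highest odds.

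**Working it through.** **1. The plan's own figure.** D.13 gives 16%, 16% and 30%, with 50 per arm:

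50×0.16 + 50×0.16 + 50×0.30 = 8 + 8 + 15 = 31; 31/150 = 20.7%.

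This reproduces ~20% (0.20×150 = 30). At the 40 completers per arm in D.13 it is 24.8 of 120, the same proportion. D.12.3 and D.13 therefore agree with each other. The D.13 SVR rates (70%, 70%, 40%) point the same way: 15 + 15 + 30 = 60 failures, and 60×0.62 = 37.

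**2. The count from the SVR rates quoted for the regimens.** Inputs: 100 on ledipasvir–sofosbuvir with failure of at most 5% (D.7, D.9.6); the other 50, by subtraction, assumed to be on telaprevir with 25% failure (D.1.4); resistance in 62% of failures (B.7), or in all of them as the high case.

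| Regimen | Failures | Events at 62% | Events at 100% |
|---|---|---|---|
| New | 100×0.05 = 5 | 3.1 | 5 |
| Earlier | 50×0.25 = 12.5 | 7.75 | 12.5 |
| Total | 17.5 | 10.9 | 17.5 |

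This gives about 11–18 events, or 7–12% of 150.

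**3. Events per parameter** (intercept not counted).

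| Events | 3 quartile terms | 3 terms + 3 covariates |
|---|---|---|
| 11 | 11/3 = 3.7 | 11/6 = 1.8 |
| 18 | 18/3 = 6.0 | 18/6 = 3.0 |
| 31 | 31/3 = 10.3 | 31/6 = 5.2 |

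Three covariates is a reasonable illustration. Table 3 has 13 covariate rows; with one irrelevant candidate per row, the screen admits 13×0.2 = 2.6 on average.

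**4. Empty quartiles.** Groups of 38, 37, 38 and 37, equal risk, event count fixed. The chance that at least one quartile has no events is about 15% at 11 events and 1.6% at 18. At 30 it is below 0.1%. With 11 events some quartile must have 2 or fewer, since 11/4 = 2.75. With 18 events that happens in about 45% of datasets.

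**5. The stated procedure, simulated.** 150 participants, 13 independent covariates unrelated to resistance (an assumption), the p<0.2 screen, no adherence effect, and a likelihood-ratio test of the quartile terms at nominal 5%.

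| Expected events | At least one coefficient diverges | Quartile test rejects |
|---|---|---|
| 11 | about 21% | about 9% |
| 18 | about 3% | about 6–7% |
| 31 | under 0.1% | – |

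**The case against.** The strongest reply is that the only resistance rates the document states for this trial are 16% and 30%. They give 31 events and support ~20%. A reader might infer that the document's own rates imply only 11–18 events and that 30 is wrong; the text does not support that. The lower range needs several assumptions:

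- Registration-type SVR is applied to every participant. D.12.1 hypothesises it for the intensive arms only and expects TAU to do worse; the background sections warn of lower adherence and real-world differences. As an illustration, 90% SVR on the new regimen and 60% on the earlier one gives 10 + 20 = 30 failures and 19–30 events.
- The 62% comes from the telaprevir-era discussion and may not carry over to failures on the new regimen.
- That the other 50 took telaprevir is a subtraction; D.2 gives telaprevir only as an example.
- 18 is not a firm ceiling. D.10.3 counts most new mutations at any time point and Table 3 schedules on-treatment resistance tests, so someone who later reaches SVR could count. D.10.4 points the other way by tying the chart assays to absence of SVR.

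All of this stands, and it makes the finding one of inconsistency. It does not remove the problem: agreement between two unrevised figures does not show that either is current.

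A second reply is that resistance is already labelled exploratory. D.13 attaches that label to the comparison between arms and does not extend it to the pooled Aim 2 model.

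Third, the candidate count is uncertain. The 13 rows include drug levels, which depend on extra funding, and self-reported adherence, which is another measure of the exposure. That is fair, and it is why the simulated rates are illustrative.

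**Conclusion.** The concern holds as an unreconciled event count combined with a model that has no protection against the lower count. The document supports 31 events through its resistance rates and about 11–18 through the SVR rates it quotes for the regimens, the latter under the assumptions listed above.

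The consequences depend on which is nearer the truth. At 11 events the stated procedure is unreliable; at 18 the problem is moderate; at 31 outright divergence is negligible, but about 5 events per parameter is still thin by the usual rule of thumb (which is not a figure from the documents). A reader might go further and conclude that the odds ratios will be biased away from 1 and the intervals invalid whatever happens. The working shows divergence and an inflated rejection rate at low counts; it does not establish that broader claim.

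The point is worth acting on because Aim 2 is one of three specific aims and the repair needs no new data.

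**What to change.** 1. In D.12.3 and D.13, reconcile ~20% (and 16%/30%) with the regimen mix. Show the expected number of events as a range, about 11–31, with the assumptions behind each end.
2. In D.12.4, replace the quartile model and the p<0.2 screen with a Firth-penalised logistic model containing adherence, adherence squared and a short pre-specified covariate set that includes regimen. The squared term is needed because a linear term alone cannot test the quadratic hypothesis. Regimen belongs in the set because the quoted SVR rates imply failure of at most 5% on one regimen and 25% on the other.
3. Cap the number of terms by the observed event count. Adherence, its square and regimen alone make three parameters, or 3.7, 6.0 and 10.3 events each at 11, 18 and 31 events.
4. Report the remaining candidate factors descriptively, as penalised odds ratios one at a time, so that the part of Aim 2 concerned with factors associated with resistance is kept. The quartile table can stay as description.

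The cost is analysis wording and one short calculation. The real downside is less covariate adjustment of a non-randomised association, which leaves more room for confounding, for example by drug use or psychiatric status. Penalisation keeps the estimates finite but adds no information, so intervals will be wide if events are few.

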1. **To determine in a randomized trial whether either of two intensive on-site HCV treatment models (DOT or concurrent group treatment) provided at a methadone program is more efficacious than standard on-site treatment for enhancing adherence and virological outcomes, and decreasing drug resistance.** We will compare the proportion of subjects in each arm who: a) adhere to antiviral treatment; b) complete antiviral treatment; c) attain SVR (cure); and d) develop drug resistance.
2. **To determine the incidence and factors associated with the development of drug resistance in IDUs initiating HCV treatment.** In a pooled analysis of all subjects, we will determine what proportion of subjects develops resistance, and examine associations between adherence and resistance.
3. **To perform cost and cost-effectiveness analyses of each model of intensive on-site HCV care.** We will use empirical data to determine the total costs of providing intensive on-site or standard on-site care. A computer simulation cost-effectiveness model combining empirical and published data will be used to determine dollars per quality-adjusted life-year gained associated with intensive versus standard care.

B. SIGNIFICANCE

B.1. HCV epidemic in IDUs. HCV prevalence in injection drug users (IDUs) ranges from 70-90%, and HCV incidence ranges from 10–26 per 100 person-years.¹⁻⁴ IDUs comprise 60% of all HCV-infected persons in the U.S., and genotype-1 infections are the most prevalent (74%).⁵ In the U.S., approximately 35,000 acute HCV infections occur each year, and a 4-fold increase in the number of adults with chronic HCV is projected from 1990-2015.⁶ HCV causes up to 15,000 deaths annually, and is the leading cause of liver transplantation in the U.S.⁷⁻⁹ Until recently (6/11), HCV treatment was effective in less than 50% of patients in registration trials,¹⁰⁻¹² and much less effective (14%) in real-world urban populations.¹³ Treatment effectiveness among IDUs is crucial because IDUs remain the leading risk group for HCV infection.¹⁴

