B.2. Treatment of chronic HCV. Sustained viral response (SVR), defined as the absence of detectable virus 24 weeks after completion of therapy, reflects elimination of HCV infection because >95% of patients with such responses remain persistently free of detectable virus up to 10 years later.^{15,16} Combination pegylated interferon (IFN) and ribavirin therapy also reduces progression of liver fibrosis,¹⁷⁻²² reduces portal hypertension,²³ prevents development of liver cancer,²⁴⁻²⁶ improves quality of life,²⁷⁻²⁹ and lengthens survival.³⁰⁻³² Treatment is complex, however, because treatment limiting side effects are extremely common.^{10-12, 33-35} These include flu-like syndromes,³⁶ cytopenias¹⁰⁻¹² which may require reduction or discontinuation of medications or the administration of growth factors,^{37,38} and neuropsychiatric side effects.³⁹⁻⁴⁵ Other common side effects are anorexia, nausea, skin rash, diarrhea, arthralgias, headaches, dizziness, and impaired thought.^{10,45} Support for side effect management is a crucial feature of HCV care.

B.3. Efficacy of new HCV regimens for genotype-1 infected patients. Treatment with IFN and ribavirin has been associated with SVR rates of 40-50% in treatment-naive patients with genotype 1. In the ADVANCE trial, patients who were treated with IFN, ribavirin, and telaprevir achieved an SVR of 75%, compared to 44% in the IFN and ribavirin arm.⁴⁶ Rates of SVR were higher in telaprevir-treated patients regardless of stage of liver disease, race, or ethnicity. However, there was a two-fold higher incidence of adverse effects, including rash, nausea, and anemia, with telaprevir-based regimens compared to IFN and ribavirin.⁴⁶⁻⁴⁸ When patients discontinue treatment prior to 20 weeks, the SVR rate is markedly decreased - only 23%.⁴⁷ Support for keeping patients on treatment is also crucial to maximize rates of SVR. The FDA has recently approved treatment of genotype-1 infected patients with 12 – 24 weeks of fixed-dose (ledipasvir and sofosbuvir), and this is associated with SVR rates of >95% (www.hcvguidelines.org).

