D.1.3. Study of HCV treatment in methadone patients. In 2003, we adapted our on-site multidisciplinary HCV program to include directly-administered weekly IFN in addition to screening, assessment of treatment eligibility, psychiatric services, and on-site antiviral therapy.⁷⁹ Of 73 patients, most were Latino (67%) or African-American (12%), nearly half (49%) had used illicit substances in the 6 months before initiating treatment, 32% were HIV-infected, and current psychiatric illness was common (67%). Most (86%) completed 12 weeks of HCV treatment and 45% achieved SVR, including 40% of genotype-1 patients. Though 30% used illicit drugs during HCV treatment, there was no association between illicit drug use and virological outcomes. These results demonstrate that IDUs with complex medical and psychiatric comorbidities can be effectively treated for HCV with co-located on-site care. However, it is unknown which interventions (multidisciplinary on-site care v. DOT injections) contributed to the observed outcomes.⁷⁸⁻⁸⁰

D.1.4. Pilot RCT of directly observed HCV treatment in methadone patients. In 2008 we began a pilot RCT (K23 DA022454, PI: [name]) of modified DOT (mDOT) which extended our DOT strategy to the oral medication ribavirin. We designed this trial to test the efficacy of 2 versions of mDOT. Our primary objective was to determine whether enhanced DOT with both IFN plus ribavirin is more efficacious than standard DOT with weekly provider-administered IFN and self-administered ribavirin for improving adherence. We have completed enrollment (n=80), with 74 initiating HCV treatment. We observed significant differences in pill count adherence between the treatment arms (88% in mDOT arm vs. 77% in the treatment as usual, or TAU arm, p=0.02).¹²⁹ In addition, 81% of mDOT subjects achieved ≥ 80% adherence v. 53% in the TAU arm (p=0.09). Only 16% discontinued treatment, and among genotype-1 infected patients (n=22), 55% achieved SVR (half active drug users).¹²⁹ Of the 1st 4 subjects on telaprevir-based triple therapy randomized to DOT, pill count adherence at 4 weeks was 98%, and 3 of 4 had 4 week VL<43 IU/ml, with one subject discontinuing treatment.

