D.12.6. Cost and Cost-effectiveness Analyses. To project future HCV costs and life expectancy, we will adapt to the study population a computer simulation model of HCV disease progression that has been developed by [name] based on published data using empiric calibration methods.¹⁷¹⁻¹⁷² The model is currently being updated with data on disease progression and resource utilization from a racially diverse cohort of over 600 HCV-infected individuals cared for at Boston Medical Center, an urban public hospital system, including IDUs in methadone treatment and active IDUs.¹⁷³ The model simulates chronic HCV with fibrosis progression through 3 stages of liver fibrosis including: mild to moderate fibrosis, cirrhosis, and decompensated cirrhosis. At all stages, HCV infection is associated with increased resource utilization and decreased quality of life (QOL).^{136,186-187} When HCV infection reaches the stage of cirrhosis, individuals begin to experience increased mortality attributable to liver disease.¹⁸⁸ With successful HCV therapy, disease progression halts, and mortality, resource utilization, and quality of life returns to that of HCV un-infected individuals.¹⁸⁹ HCV-related QOL is stratified by fibrosis stage, and costs of chronic HCV care (such as hospitalizations, ED visits, and clinic visits) are identified separately for patients with and without cirrhosis and stratified by age and sex.

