We will use the model to assess the cost-effectiveness of the 3 interventions: TAU, mDOT, and CGT. Primary outcomes will be projected life-expectancy, quality-adjusted life-expectancy (QALYs), lifetime costs, and incremental cost-effectiveness ratios measured in \$/QALY. We will forecast health and cost outcomes of each intervention for a hypothetical cohort of HCV patients using baseline study data on fibrosis, age, sex, and alcohol use, and study outcome data for each intervention including SVR, resistance, and retention in care. We will explore the potential impact of resistance mutations by varying the efficacy of subsequent HCV retreatment for patients with resistance who choose to be retreated. Lifetime costs will include the costs of the intervention received as well as projected future costs of HCV care depending on treatment effectiveness. Incremental cost effectiveness ratios will be calculated for TAU compared to no treatment and for mDOT and CGI compared to the next most expensive intervention, with costs and QALYs discounted at 3% annually according to standard practice.¹⁷³ The resulting ratios will be compared to a threshold of \$100,000 per QALY.¹⁷⁴⁻¹⁷⁵ To explore uncertainties in our results, we will perform one and 2-way sensitivity analyses on key input variables (e.g. probability of SVR and intervention cost) and probabilistic sensitivity analyses (PSAs) using second order Monte Carlo simulation on multiple variables.¹⁷⁶ For PSAs we will perform 1,000 simulations of a cohort of 100,000 individuals. The result will be a distribution of 1,000 model-based outcomes with a median and interquartile range that reflects underlying uncertainty in critical model parameters.

D.13 Power considerations Assuming a conservative attrition rate of 20%, 50 subjects per arm will begin the study, but 40 subjects per arm will complete it. For power calculations for repeatedly measured continuous or binary adherence outcomes, we will use the expected number of observations per subject. The power analysis is conducted based on the omnibus testing of equality across the three groups. It follows that at least one of the post-hoc pair-wise tests is powered to be rejected by this study design.

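### D.12.6 describes no reinfection after SVR in a population the protocol presents as at continuing risk, so QALYs per cure are overstated by an amount that depends on an unstated rate

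*Combined protocol and SAP*

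**What the plan says.** D.12.6 adapts an existing simulation model to the study population. On its structure: "The model simulates chronic HCV with fibrosis progression through 3 stages of liver fibrosis". On cure: "With successful HCV therapy, disease progression halts, and mortality, resource utilization, and quality of life returns to that of HCV un-infected individuals". The cohort is to be projected "using baseline study data on fibrosis, age, sex, and alcohol use, and study outcome data for each intervention including SVR, resistance, and retention in care". Drug use is not among these inputs. Retreatment comes up once, where the effect of resistance is explored by "varying the efficacy of subsequent HCV retreatment for patients with resistance who choose to be retreated". One-way, two-way and probabilistic sensitivity analyses are planned; SVR probability and intervention cost are given as examples. Costs and QALYs are discounted at 3% a year, and ratios are judged against $100,000/QALY. D.12.5 hypothesises that CGT versus TAU and mDOT versus TAU both fall below that threshold.

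Other sections bear on risk after cure:

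- B.1, on injection drug users generally: "HCV incidence ranges from 10–26 per 100 person-years".
- B.2, on durability of response, not stated for drug users: ">95% of patients with such responses remain persistently free of detectable virus up to 10 years later".
- D.1.3, on the earlier on-site cohort: "Though 30% used illicit drugs during HCV treatment". In the same cohort 49% had used illicit substances in the six months before treatment.

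Reinfection is not mentioned anywhere in the documents, including the limitations in D.14.

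**The concern.** Aim 3 asks what an extra cure is worth over a lifetime, in patients recruited because they inject or have injected drugs. If the model keeps every cured patient at uninfected health, each SVR earns its full lifetime gain. Any positive reinfection rate shortens that gain. For an arm that costs more and cures more, the QALY denominator shrinks and the ratio rises. The cost side moves the same way: D.12.6 also returns resource use to uninfected levels, so reinfection would erode those savings.

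The two rates in the protocol that could inform the time after cure are far apart, and the plan does not say which applies, or whether either does. A parameter with no described transition cannot be varied, so the sensitivity analyses as described do not fill the gap.

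**Working it through.** The documents give no cost-effectiveness ratio, QALY gain per cure, intervention cost or reinfection rate, so there is no figure of the plan's own to reproduce. The check asks how much of the benefit of a cure survives at different reinfection rates.

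**Inputs from the documents.** Discount rate r = 3% (D.12.6); mean age 47 and 75% of HCV-infected clinic patients chronic (D.4); incidence 10–26 per 100 person-years (B.1); more than 95% virus-free up to 10 years (B.2); illicit use 30% during and 49% before treatment (D.1.3).

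**Assumptions.** T = 25 years of remaining life, constant reinfection rate λ, no retreatment, and benefit proportional to discounted virus-free years.

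**Step 1: the rate implied by B.2.** λ = −ln(0.95)/10 = 0.0051, or about 0.5 per 100 person-years at most. The B.1 range is about 20 to 50 times higher (10/0.51 and 26/0.51).

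**Step 2: share of benefit retained.**

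f = [(1 − e^(−(r+λ)T))/(r+λ)] / [(1 − e^(−rT))/r]

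The denominator is (1 − e^(−0.75))/0.03 = 17.59. At λ = 0.05 the numerator is (1 − e^(−2))/0.08 = 10.81, so f = 10.81/17.59 = 0.61. With incremental cost unchanged, the ratio is multiplied by 1/f.

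| λ per 100 person-years | f | 1/f |
|---|---|---|
| 0.5 (from B.2) | 0.95 | 1.06 |
| 2 (assumed) | 0.81 | 1.23 |
| 5 (assumed) | 0.61 | 1.63 |
| 10 (low end of B.1, unscaled) | 0.42 | 2.38 |
| 26 (high end of B.1, unscaled; extreme) | 0.20 | 5.10 |

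At λ = 10, f is 0.47 for T = 20 and 0.38 for T = 30.

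**Step 3: scaling B.1 to this population.** Taking illicit use as a rough proxy for exposure (not all of it is injecting) and 75% for chronicity: 10 × 0.30 × 0.75 = 2.3 and 26 × 0.49 × 0.75 = 9.6 per 100 person-years. At 25 years f is 0.79 and 0.43, so the ratio rises about 1.3- to 2.3-fold.

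**Step 4: structural check.** A small state-transition model was run over 40 years. Its rates are assumed: 2.5% a year to cirrhosis, 5% to decompensation, 2% background mortality, 3% and 15% extra mortality in cirrhosis and decompensation. Utilities were 1, 0.9, 0.8 and 0.65. It retained 0.94, 0.80, 0.61, 0.43 and 0.22 of the QALY gain at the five rates in the table, close to f.

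**Step 5: does the threshold conclusion change?** It depends on the starting ratio, which the documents do not give. An illustrative $60,000/QALY becomes 60,000/0.81 ≈ $74,000 at 2 per 100 person-years and 60,000/0.61 ≈ $98,000 at 5. An illustrative $20,000/QALY is still only 20,000/0.42 ≈ $48,000 at 10.

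**Step 6: can the trial estimate the rate?** Viral load is scheduled at follow-up weeks 12 and 24. On the D.13 assumptions, cures number 40 × (0.70 + 0.70 + 0.40) = 72, giving 72 × 12/52 ≈ 17 person-years. If all 150 were cured, it is 150 × 12/52 ≈ 35. At 2 per 100 person-years that is 0.3 to 0.7 expected events. With no events, the exact 95% upper limit is 3.69/16.6 ≈ 22 or 3.69/34.6 ≈ 11 per 100 person-years (3.69 = −ln 0.025). These data cannot set the rate.

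**The case against.** D.12.6 is a summary of a model documented elsewhere, to be adapted to this population and updated with a cohort that includes patients on methadone and active injectors. A reader might infer that the model definitely makes cure permanent. The text does not say so: it describes the state after SVR, not how long it lasts, and the lists of sensitivity variables are open. That stands. The supportable statement is that no route back to infection is described.

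A reader might also apply 10–26 per 100 person-years to cured trial patients. That figure is general incidence in injection drug users, not reinfection after SVR in patients on methadone. B.1 and B.2 describe different groups, so they do not contradict each other. Unscaled, 26 is an extreme scenario only.

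Nor does all QALY gain between arms have to come through SVR, since resistance and retention in care also feed the model. The shares above apply to the part that does.

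Finally, B.8 expects the added cost of the intensive models to be small relative to treatment, which may leave their ratios well below the threshold. The model as described also credits no averted onward transmission, although reducing transmission is a stated motivation of the study. That omission understates the value of cure and works in the opposite direction. Both points limit what can be concluded. Neither is a reason to leave reinfection out: one unmodelled effect does not justify another, and D.12.6 also compares TAU with no treatment, where B.8 puts drug cost alone at possibly over $90,000.

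**Conclusion.** The point holds as an unaddressed structural assumption in the Aim 3 model. Followed as described, the model overstates QALYs per cure and, for this one omission, understates the ratios of costlier, more effective arms. The size rests on an assumed rate. Over 25 years, at a constant rate and without retreatment, the loss is about 5% of the benefit at 0.5 per 100 person-years, 19% at 2, 39% at 5 and 58% at 10.

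It is tempting to conclude that the $100,000/QALY verdict is biased towards the intensive models. The documents do not support that. They fix neither the SVR difference that will be seen, nor the QALYs per cure, nor the intervention cost, and the net direction is open while transmission is also left out. Aims 1 and 2 are not affected.

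**What to change.** In D.12.6:

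1. Add a transition from SVR back to chronic HCV at the same fibrosis stage, and amend the sentence on the state after cure to match.
2. Allow retreatment of reinfection in the model, with its cost and effect, not only retreatment of patients with resistance.
3. Take the base-case rate from published reinfection data for patients on opioid agonist treatment, and justify it for this population.
4. Name the rate in the one-way and probabilistic analyses, for example 0 to 10 per 100 person-years with 26 as an extreme, and report the rate at which each ratio crosses $100,000/QALY.
5. Report recurrent viraemia between follow-up weeks 12 and 24 descriptively only. The 17 to 35 person-years are too few to set the rate. Genotype is scheduled only at baseline and no rule is given for telling late relapse from reinfection.
6. State in D.14 that averted transmission is not modelled, if that is so.

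The cost is one extra transition, the modelled retreatment option and a little more modelling work. The ratios will look less favourable. No new patients, visits or tests are needed.
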